Secondary Estimand #3	Adult subjects with FD as defined by the inclusion and exclusion criteria in the study protocol with GI symptoms at baseline.	Lucerastat (dose ranging from 250 mg to 1000 mg b.i.d. based on subject's eGFR value) as monotherapy which will be compared to placebo.	Change from baseline to Month 6 in the number of days with at least 1 stool of a Bristol Stool Scale consistency Type 6 or 7.	Treatment policy, i.e., all collected endpoint data are used regardless of premature treatment discontinuation or use of other medication (e.g., medication used to treat/prevent diarrhea).	Win ratio of change from baseline to Month 6 between lucerastat and placebo.

b.i.d. = twice daily; BPI-SF3 = Brief Pain Inventory – Short Form item 3; eGFR = estimated glomerular filtration rate; ERT = enzyme replacement therapy; FD = Fabry disease; Gb3 = globotriaosylceramide; GI = gastrointestinal; NRS-11 = 11-point numerical rating scale.

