#### 15.3.2 Change from baseline to Month 6 in the number of days with at least 1 stool of a BSS consistency Type 6 or 7 in subjects with GI symptoms at baseline

This endpoint will be analyzed using the mFAS-GIS. All available data will be used regardless of occurrence of ICEs such as premature treatment discontinuation or changes

in background medication. Subjects with a missing baseline value will be excluded from the analysis.

The change from baseline to Month 6 in the number of days with at least 1 stool of a BSS consistency Type 6 or 7 will be analyzed using a non-parametric rank analysis of covariance [Quade 1967, Koch 1982, Koch 1990, Stokes 2012] adjusted for the baseline value and stratified by sex and ERT treatment status at screening, as follows:

1. Produce standardized ranks for the baseline variable (covariate) and the change from baseline to Month 6 variable (response) within each stratum. Standardized ranks are used to adjust for the fact that the number of subjects differ among strata.
2. Fit a separate linear regression model for each stratum with the standardized ranks of the baseline variable and the change from baseline to Month 6 variable as independent and dependent variable, respectively. Retain the regression residuals.
3. Apply the stratified CMH mean score test using the residuals as scores to compare treatment groups. The p-value from this test will be used to test the null hypothesis.

The three steps will be implemented using the following SAS® code.

```
/* 1) Produce standardized ranks for covariate BASE and response variable CHG - ensure to
impute ranks for CHG as described in the text below prior to this step */
* nplus1 option requests fractional ranks by using denominator n+1 where n is the strata-
specific sample size;
* ties=mean option requests midranks;
proc rank data = input nplus1 ties = mean out = ranks;
  by sex ert_status;
  var base chg;
run;

/* 2) Linear regression for each stratum on standardized ranks; output residuals */
proc reg data = ranks noprint;
  by sex ert_status;
  model chg = base;
  output out = residual r = resid;
run;

/* 3) Stratified mean score test, using values of residuals as scores, to compare
treatment groups */
proc freq data = residual;
  tables sex*ert_status*treatment*resid / noprint cmh2;
run;
```

The rank analysis of covariance does not provide an interpretable treatment effect estimate. Therefore, the magnitude of the treatment effect will be estimated using the unadjusted

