non-parametric win ratio [Wang 2016] between lucerastat and placebo with corresponding 95% CI, derived via bootstrap (100,000 samples) using the bias-corrected method [Carpenter 2000] on the log-transformed win ratio. The rejection of the null hypothesis will be solely based on the p-value from the rank analysis of covariance and not the 95% CI of the unadjusted win ratio estimator.

Bootstrapping will be implemented using the following SAS® code:

```
proc surveyselect data=ranks out=boot seed=197 method=urs samprate=1 reps=100000 outhits;  
  strata treatment;  
run;
```

Aligned with the treatment policy strategy, all subjects with a valid value for the change from baseline to Month 6 will be ranked based on these values (such that larger decreases are associated with better ranks). Subjects with a missing value for the change from baseline to Month 6 will be assigned worse ranks than subjects with available change from baseline to Month 6 values based on their last available change from baseline value prior to Month 6. Subjects with a non-missing baseline value but no post-baseline data will be assigned the worst rank. Mid-ranks are used in the event of ties.

To explore the robustness of inferences from the main analysis described above to deviations from its assumptions regarding missing data, the above analysis will be repeated as a sensitivity analysis using the following rules for ranking of subjects with missing data. As above, subjects with a missing value for the change from baseline to Month 6 will be assigned worse ranks than subjects with available change from baseline to Month 6 values, based on their last available change from baseline value prior to Month 6. However, these subjects will then be divided into four quarters using the first quartile, median and third quartile of their last available change from baseline value. Within each quarter, lucerastat subjects will be assigned worse ranks than placebo subjects. Lucerastat subjects with a non-missing baseline value but no post-baseline data will be assigned the worst rank. Placebo subjects with a non-missing baseline value but no post-baseline data will be assigned the second worst rank. Mid-ranks are used in case of ties.

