The win ratio together with its 95% CI will also be derived within each subgroup defined in Section 6 (using the ranking for the main analysis described above), and presented in a forest plot. Bootstrapping will be performed separately for each subgroup to ensure constant numbers of subjects by treatment group within each bootstrap sample, using the following SAS® code:

```
proc surveyselect data=ranks out=boot seed=197 method=urs samprate=1 reps=100000 outhits;  
  strata treatment subgroup;  
run;
```

The following supportive analyses will be performed:

- The same approach (CMH test) as described in Section 15.2.5.1 will be used to analyze a response variable (yes/no) defined as a reduction from baseline to Month 6 of at least 50% in the number of days with at least one stool of a BSS consistency Type 6 or 7 in subjects who have diarrhea at baseline.
- The same approach (MMRM) as described in Section 15.2.5.5 will be used to characterize the treatment effect over time.

Patterns of missingness will be summarized as described in Section 15.2.2. An eCDF plot of the absolute change from baseline to Month 6 by treatment arms will be provided as well.

Descriptive summary statistics of the absolute values and changes from baseline will be provided on the mFAS-GIS and the mFAS.

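### The bootstrap code for the diarrhea win ratio resamples a data set in which the change has been overwritten by a within-stratum rank, contradicting the unadjusted win ratio and missing-data order in the text

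*SAP*

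**What the plan says.** SAP Table 1 gives the population-level summary for Secondary Estimand #3 as "Win ratio of change from baseline to Month 6 between lucerastat and placebo". SAP 15.3.2 tests the endpoint by stratified rank ANCOVA and reports the win ratio as the effect size, because the rank ANCOVA gives no interpretable estimate. The win ratio is described as unadjusted, and rejection rests on the rank-ANCOVA p-value, "not the 95% CI of the unadjusted win ratio estimator". Protocol 10.3.3.2 says the same.

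On missing data, SAP 15.3.2 says that subjects without a Month 6 change "will be assigned worse ranks than subjects with available change from baseline to Month 6 values". This is an ordering across all subjects.

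The code then runs as follows:
- Step 1 in words: "Produce standardized ranks for the baseline variable (covariate) and the change from baseline to Month 6 variable (response) within each stratum".
- Step 1 in code: "proc rank data = input nplus1 ties = mean out = ranks", run by sex and ERT status on `base` and `chg`. A comment above it tells the programmer to "impute ranks for CHG as described in the text below prior to this step".
- The overall bootstrap: "proc surveyselect data=ranks out=boot seed=197 method=urs samprate=1 reps=100000 outhits", stratified by treatment.
- The subgroup bootstrap resamples the same data set, stratified by treatment and subgroup. The text says the subgroup win ratios are derived "using the ranking for the main analysis described above".

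The step that computes the win ratio from the resamples is not printed.

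**The concern.** Step 1 has no RANKS statement, so PROC RANK writes the ranks back under the names `base` and `chg`. In `ranks`, `chg` is therefore no longer the change, nor the pooled order with missing subjects at the bottom. It is the subject's fractional position within his or her own stratum. A win ratio compares every lucerastat subject with every placebo subject, including pairs from different strata, and for those pairs within-stratum positions are not comparable.

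If the code is followed with `chg` as the analysis variable, the win ratio, its 95% CI and the subgroup forest plot would not estimate the quantity that Secondary Estimand #3 defines. The hypothesis test is not at stake.

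**Working it through.** The plan states no figure on this point, so there is none to reproduce. The check is a trace of the code, hand examples, and simulation under stated assumptions.

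**1. What `chg` is in `ranks`.** Step 1 ranks within stratum with denominator n+1 and gives the ranks no new names. Step 2 confirms the result: it regresses `chg` on `base` from this data set and labels both as standardized ranks. The missing-data order is placed in CHG before step 1, in the variable that step 1 then replaces. Order within a stratum is preserved, so only pairs from different strata are affected.

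**2. Reversal.** A lower value is better (larger decrease in days). Take changes of -10, -8, -6, -4 in one stratum and +2, +4, +6, +8 in another. With n = 4, rank/(n+1) gives 0.2, 0.4, 0.6, 0.8 in both. A subject who improved by 4 days (0.8) then loses to one who worsened by 2 days (0.2). For the same reason, equal changes in different strata can become wins or losses.

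**3. Missing-data rule.** In a stratum of 8 with 3 missing, the missing subjects receive 6/9 = 0.667, 7/9 = 0.778 and 8/9 = 0.889. In a stratum of 30 with none missing, values are k/31:
- k/31 > 0.667 for k = 21 to 30: 10 observed subjects rank worse.
- k/31 > 0.778 for k = 25 to 30: 6 observed subjects rank worse.
- k/31 > 0.889 for k = 28 to 30: 3 observed subjects rank worse.

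**4. Effect on a win ratio (assumed data, 5 × 3 = 15 pairs).** Stratum A: lucerastat -10 and missing; placebo -6. Stratum B: lucerastat -2, 2, 4; placebo 0, 3.

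| Basis | Wins | Losses | Ties | Win ratio |
|---|---|---|---|---|
| Pooled order, as in the text | 6 | 9 | 0 | 6/9 = 0.67 |
| `chg` as stored in `ranks` | 7 | 7 | 1 | 7/7 = 1.00 |

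The missing subject in A gets 3/4 = 0.75 and ranks ahead of the observed worst subject in B at 5/6 = 0.83.

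**5. Size by simulation.** The documents give no SD, effect or stratum difference for this endpoint, so all of these are assumptions. The size is 0.70 × 118 = 82.6, taken as 82, from the 70% expectation in Protocol 10.5 and the 118 randomized in SAP 2. Further settings: 2:1 allocation, four strata (20/30/20/30%), SD 6 days, effect 0 to -4 days, stratum means 0 to 6 days apart, 0 or 30% unchanged, 0 to 10% missing overall or concentrated in some strata; 72 settings of 1000 to 3000 trials.
- No effect: both versions average about 1.0.
- Otherwise the average shift runs from -7% (2.00 becomes 1.87) to +4% (1.84 becomes 1.91).
- Single-trial win ratios differ by more than 10% in 5-30% of trials.
- In a random 30% subgroup (about 25 subjects) they differ by more than 10% in 47-68% of trials and by more than 20% in 18-42%.
- With about 8 missing subjects, at least one ranks no worse than an observed subject in 93-99% of trials, but this is only 2-6% of missing/observed pairs.

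A second simulation used the 69 subjects (46:23) of Protocol 10.5, with assumed strata of 24/12/20/13, SD 6, effect 4 days, 25% zero changes and 0-20% missing. With no stratum difference, the median win ratio was 1.56-2.01 on the pooled order and 1.54-1.90 on stored ranks. With 6 days between adjacent strata, it was 1.30-1.49 and 1.45-1.74. Across settings, the 5-95% range of the within-trial ratio of the two was about 0.83 to 1.45. Ties fell from about 6-11% of pairs to 2-3%. About 2% of missing/observed pairs broke the rule.

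**The case against.** The strongest reply is that PROC SURVEYSELECT only draws rows. It computes no win ratio and names no analysis variable. PROC RANK carries other columns through, so `ranks` could also hold a pooled order variable, and a programmer following the text could use it. The SAP code is visibly excerpted: the Jump to Reference code in 15.2.4.2 reads a data set that no printed step creates, and variable names vary between blocks. The governing text is itself correct.

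This stands as a limit: a wrong reported win ratio is conditional on the unprinted step reading `chg`. It does not remove the conflict. The SAP names no other order variable, and its own comment puts the pooled order in the variable that is overwritten.

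The consequence is also limited. This is the last of four hypotheses, the p-value is untouched, and the responder analysis and MMRM do not use this data set. However, the responder analysis covers only subjects with diarrhea at baseline, and the MMRM is parametric for an endpoint moved to a non-parametric analysis because of suspected non-normality.

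Sampling error is larger than most of the differences. With 55:27 and no ties or effect, the 95% factor is exp(1.96 × 4 × √(83/(12 × 55 × 27))) = exp(0.535) ≈ 1.7 either way. That is fair context, but it does not justify estimating a different quantity. Finally, the subgroup figures come from a random subset, whereas the sex and ERT subgroups each contain only two of the four strata. They are illustrative.

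**Conclusion.** The concern holds. As printed, the code conflicts with the text of SAP 15.3.2 and with Table 1: the only change variable named in the resampled data set is a within-stratum rank, while the estimand calls for a pooled, unadjusted comparison with missing subjects at the bottom. The conflict covers the win ratio, its 95% CI and the subgroup forest plot. It does not touch the rank-ANCOVA p-value or the type I error.

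The average distortion is likely to be modest unless strata differ widely. It can be material in a single trial, particularly in small subgroups. Its direction varies with stratum differences, ties and missingness, so it could not be corrected afterwards from the reported figures. All sizes rest on assumed distributions; the code conflict does not.

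**What to change.** State in SAP 15.3.2 that the win ratio and its bootstrap, overall and by subgroup, use one pooled ranking of the change across all subjects with the missing-data rule applied, and that within-stratum ranks serve the rank ANCOVA only.

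In both SURVEYSELECT calls, replace `ranks` by the pre-step-1 data set `input`, where CHG already carries the pooled order, or by a separately named copy. Alternatively, add a RANKS statement in step 1 so that `chg` survives, and use the new rank names in step 2. Print the short step that counts wins, losses and ties, so that the variable it reads is explicit.

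The cost is one data set name in two calls, a few lines of code and one sentence. The hypothesis test does not change.

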### 15.3.3 Change from baseline to Month 6 in plasma Gb3

This absolute change endpoint will be analyzed using the mFAS. All available data will be used regardless of occurrence of ICEs such as premature treatment discontinuation or changes in background medication.

Missing data will be imputed applying an MI approach assuming MAR similarly to that described in Section 15.2.4.1. The imputation model includes the baseline value, the two stratification factors (sex and ERT treatment status at screening), Month 1, Month 3, Month 5, and Month 6 values and treatment group.

Subjects with the baseline value missing will be excluded from this analysis.

The MI procedure will be implemented by the following SAS® code:

```
proc mi data=h nimpute=500 seed=32767 min=. . . . 0 0 0 0 minmaxiter=1000000out=h2;  
  mcmc impute = monotone;  
  var treatment sex ertstatus baseline y1 y3 y5 y6;  
run;  
proc mi data=h2 nimpute=1 seed=32767 min=. . . . 0 0 0 0 minmaxiter=1000000out=h3;  
  by _imputation_;  
  class treatment sex ertstatus;  
  var treatment sex ertstatus baseline y1 y3 y5 y6;  
  monotone regression;  
run;
```

The MAR assumption can be considered reasonable for this endpoint as it is an objective assessment and not patient-reported and therefore less likely to be related to reasons for study withdrawal. In addition, patients, physicians as well as the sponsor are blinded to the plasma Gb3 results until after database lock and a lower amount of missing data is expected compared to the abdominal pain and stool consistency endpoints.

The analysis, within each imputed dataset, will be performed using an ANCOVA as described in Section 15.2.3.

Results from these analyses are combined using Rubin's methodology [Rubin 1987] implemented in SAS® PROC MIANALYZE.

The mean difference in changes from baseline to Month 6 between lucerastat and placebo together with its two-sided 95% CI and p-value will be reported.

To explore the robustness of inferences from the main analysis described above to deviations from its underlying assumptions regarding the nature of missing data, control-based MI assuming MNAR using the CR and J2R approaches [described in Sections 15.2.3 and 15.2.4.2] will be applied.

Subgroup analyses will be performed similarly to those described in Section 15.2.6 by including the respective subgroup and subgroup by treatment interaction in the ANCOVA.

A supportive analysis using an MMRM approach will be conducted to characterize the treatment effect over time such that change in plasma Gb3 will be analyzed on all available data from all scheduled visits without replacement of missing values.

The model will enable:

- Estimation of the treatment difference (lucerastat minus placebo) in the mean changes from baseline to Month 6 along with the corresponding 95% CI;
- Characterization of the patterns of change over time in the mean change from baseline in Gb3 by treatment group.

The main analysis described above (MI assuming MAR + ANCOVA) will be repeated (with the log-baseline as covariate) on log-transformed values (i.e.,  $\log[\text{post-baseline}] - \log[\text{baseline}] = \log[\text{post-baseline} / \text{baseline}]$ ) leading via the back transformation  $x \rightarrow ((e^x - 1) \times 100)$  to treatment group results expressed as percent change from baseline and treatment effect estimate expressed as the ratio of the percent change between lucerastat and placebo. The log-transformation will only be applied after values have been imputed on the original scale, i.e., the imputation step is identical to the main analysis described above.

Patterns of missingness will be summarized as described in Section 15.2.2. An eCDF plot of the absolute change from baseline to Month 6 by treatment arms will be provided as well.

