The TQT study was split into two parts: Part A was a double-blind, placebo-controlled study in healthy male subjects to determine the suprathreshold dose of lucerastat to be used in Part B. Part B was a randomized, double-blind (for lucerastat), placebo-controlled, four-way crossover study including an open-label positive control in healthy male and female subjects to assess the effect of single therapeutic and suprathreshold doses of lucerastat on the QT/QTc interval duration. In Part A, 6 subjects received a single oral dose of 2000 mg lucerastat on Day 1 and a single oral dose of 4000 mg lucerastat on Day 3, whereas 2 subjects received placebo both on Days 1 and 3. In Part B, 36 subjects were enrolled. Subjects received, in a random sequence, single oral doses of 1000 mg lucerastat (anticipated therapeutic dose), 4000 mg lucerastat (suprathreshold dose), 400 mg open-label moxifloxacin (positive control to assess assay sensitivity), and placebo. Based on concentration-QTc analysis, a QTc according to Fridericia's formula (QTcF) effect of clinical concern (i.e., above 10 ms) could be excluded up to lucerastat plasma concentrations of approximately 34 $\mu\text{g/mL}$. The results constituted a negative TQT study, demonstrating that lucerastat up to a single dose of 4000 mg does not have any clinically relevant liability to prolong the QT interval or any clinically relevant effect on other ECG parameters.

In the exploratory Phase 1b study, a marked change in biomarkers was observed in subjects with FD who received 1000 mg b.i.d. lucerastat on top of ERT, with a mean percentage change from baseline (standard deviation [SD]) of -49% (17), -33% (13), and -55% (10)

in plasma levels of glucosylceramide (GlcCer), lactosylceramide (LacCer), and Gb3, respectively, at Week 12.

Urinary Gb3 was also decreased by 53% (21) at Week 12.

There was no change in plasma GlcCer, LacCer or Gb3 in the control group. No significant changes were observed for plasma lysoGb3 in either group. The concomitant decrease in GlcCer, LacCer, and Gb3 confirms GCS inhibition and α -GalA substrate reduction with lucerastat in subjects with FD.

More detailed information can be found in the IB [[Lucerastat IB](#)].

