1.2.4 Lucerastat dose rationale

Based on the nonclinical data from studies in wild-type mice and Fabry mice [[Lucerastat IB](#)], it was hypothesized that achieving plasma drug concentrations equal to or above the inhibition constant (K_i) for inhibition of human GCS for at least 80% of the time during a 24 h dosing interval is needed to achieve relevant substrate reduction and subsequent decreases of plasma Gb3 levels in subjects with FD. The exploratory Phase 1b study in subjects with FD receiving ERT confirmed that treatment with a dose of lucerastat 1000 mg b.i.d. for 12 weeks was adequate, resulting in (i) plasma lucerastat concentration above the K_i for 98% of the time of a dosing interval, (ii) marked and favorable PD effects (e.g., a decrease in plasma Gb3 level of 55%), and (iii) good safety and tolerability [[Lucerastat IB](#)].

The nonclinical and clinical safety data and the resulting safety margins / exposure ratios are considered to adequately support the safe use of lucerastat at doses up to 1000 mg b.i.d. in long-term clinical studies in subjects with FD, taking into account the limited and/or species-specific toxicity in animals, the reversibility of the findings, and the severity of the disease.

Based on available nonclinical and clinical data, a dosing regimen of lucerastat 1000 mg b.i.d. is considered adequate to potentially achieve a clinical benefit while maintaining long-term safety and tolerability in subjects with FD.

In subjects with moderate renal function impairment increased systemic exposure was observed, hence dose adjustment is required in this population [see Section [5.1.2](#)].

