## 2 STUDY DESIGN AND FLOW

This is a prospective, multi-center, double-blind, randomized, placebo-controlled, parallel-group, Phase 3 study.

118 adult subjects with Fabry disease (FD) exhibiting Fabry-associated pain of moderate to severe intensity were randomized in a 2:1 ratio to either lucerastat (approximately 79 subjects) or placebo (approximately 39 subjects).

Treatment allocation was stratified by

- sex
- and
- enzyme replacement therapy (ERT) treatment status at screening
    - “pseudo-naïve” / “treatment naïve” (not treated in last 6 months / never treated)
- vs
- “switch” (subjects treated with ERT at screening).

Once randomized, subjects entered a 6-month, double-blind treatment period. Approximately 36 subjects were included worldwide in a PK profile sub-study.

All English-speaking subjects in the US and Canada were asked to participate in an exit interview sub-study; subjects who accepted performed this interview as soon as possible after the Month 6 or End-of-Treatment (EOT) visit, ideally within 2 weeks.

No interim analysis was planned.

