  mcmc impute = monotone;
  var treatment sex ertstatus baseline y1 -- y6;
run;
proc mi data=h2 nimpute=1 seed=32767 minimum = . . . . 0 0 0 0 0 0 maximum = . . . . 10
10 10 10 10 10 minmaxiter=1000000out=h3;
  by _imputation_;
  class treatment sex ertstatus;
  var sex ertstatus bsl y1 -- y6;
  mnar model (y1 -- y6 / modelobs=(treatment="placebo"));
  monotone regression;
run;

```

An analysis of covariance (ANCOVA) model will then be used to analyze this endpoint on each imputed dataset. The following terms will be included in the model: baseline value, the two stratification factors (sex and ERT treatment status at screening), and the treatment group. This analysis will be implemented by the following SAS® code:

```

proc mixed;
  by _imputation_;
  class sex ertstatus treatment;
  model change = sex ertstatus bsl treatment;
  lsmeans treatment / cl pdiff;
run;

```

Uncertainty in the imputations will be reflected appropriately in the analysis by combining the results on each imputed dataset using Rubin's methodology [Rubin 1987]. The final estimate is the mean of the 500 per-imputation estimates and the final variance is the sum of the average within-imputation variance and  $(1 + 1 / 500)$  times the between-imputation variance [Rubin 1987]. From the final point estimate and variance, the 95% CI will be determined.

The results aggregation of the MI procedure after analysis of the 500 complete datasets will be implemented by the following SAS® code:

```

proc mianalyze data = <ods output lsmeans from proc mixed>;
  ods output parameterestimates=ls_m_comb;
  by treatment;
  modeleffects estimate;
  stderr stderr;
run;

proc mianalyze data = <ods output diffs from proc mixed>;
  ods output parameterestimates=diff_comb;
  modeleffects estimate;
  stderr stderr;
run;

```

The mean difference in changes from baseline to Month 6 between lucerastat and placebo together with its two-sided 95% CI and p-value will be reported.

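### The confirmatory plasma Gb3 ANCOVA pools one residual variance and one baseline slope across 2:1 arms, so its 95% CI can mis-cover when the drug works; a robust standard error would correct this (minor)

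*SAP*

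**What the plan says.** Plasma Gb3 is tested second in the fixed sequence (SAP 15.1). SAP 15.3.3 sets the scale and population: "This absolute change endpoint will be analyzed using the mFAS". After multiple imputation under MAR, "The analysis, within each imputed dataset, will be performed using an ANCOVA as described in Section 15.2.3". The code in SAP 15.2.3 is a MIXED call with the statement "model change = sex ertstatus bsl treatment". It has no treatment-by-baseline term, no arm-specific variance and no robust option. The committed output is explicit: "The mean difference in changes from baseline to Month 6 between lucerastat and placebo together with its two-sided 95% CI and p-value will be reported".

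Allocation is 2:1, with 118 randomized, about 79 to lucerastat and 39 to placebo (SAP 2). On the expected effect, Protocol 1.2.3 reports a mean percentage change in plasma Gb3 of −55% (SD 10) at Week 12 on lucerastat, and for controls "There was no change in plasma GlcCer, LacCer or Gb3 in the control group".

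SAP 15.3.3 also plans a supportive repeat on the log ratio, and CR and J2R sensitivity analyses. No Gb3 baseline spread, variance or power is stated, and no discontinuation rate.

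**The concern.** The sponsor summarizes the Gb3 effect as a percentage. If the fall is in fact proportional to baseline, absolute change follows baseline in the lucerastat arm and not in the placebo arm, and the two arms have different scatter around a shared line. A pooled standard error tolerates that when the arms are equal in size. It does not when they are 2:1, because the larger arm dominates the pooled variance while the smaller arm dominates the true sampling error. What is at stake is the stated precision of the key pharmacodynamic estimate.

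**Working it through.** **Plan's own figures.** There is none for Gb3. The only confirmatory power figure is for the primary endpoint (Protocol 10.5). With 66 v 33, difference 2 and SD 3, the noncentrality is 2/(3·√(1/66+1/33)) = 3.127 on 97 df, which gives 87.2% as stated. The equal-variance assumption there is made for the primary endpoint only.

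**Inputs from the documents.** 79:39; lucerastat ratio to baseline 0.45 with SD 0.10; placebo ratio 1.

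**Assumed inputs.** Baseline CV 0.3–0.8; placebo noise CV p, mainly 10–22%; a share d of lucerastat subjects who revert to placebo-like values. The value 22% equals lucerastat's own relative noise, 0.10/0.45.

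**Analytic check at baseline CV 0.5, d = 0.** Set mean baseline to 1, so Var(B) = 0.25 and E(B²) = 1.25.

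- The slopes of change on baseline are −0.55 (lucerastat) and 0 (placebo). The fitted common slope is about (79/118)(−0.55) = −0.368.
- Lucerastat residual variance: 1.25×0.10² + (0.55−0.368)²×0.25 = 0.0208.
- Placebo residual variance: 1.25p² + 0.368²×0.25, which is 0.0956 at p = 22.2% and 0.0464 at p = 10%.
- Model SE = √[pooled variance×(1/79+1/39)]. True SE = √[0.0208/79 + placebo variance/39].
- At p = 22.2% the pooled variance is (79×0.0208+39×0.0956)/118 = 0.0455, so the model SE is 0.0417 against a true SE of 0.0521. The ratio is 0.80 and coverage is about 2Φ(1.96×0.80)−1 = 88%.
- At p = 10% the SEs are 0.0335 and 0.0381. The ratio is 0.88 and coverage about 91%.

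**Role of allocation.** At 59:59 and p = 22.2% the common slope is −0.275 and the variances are 0.0806 and 0.0314. Model and true SE are then both √[(0.0806+0.0314)/59] = 0.0436. Simulated coverage at 1:1 is 91–95%.

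**Role of reversion.** Take d = 10% and p = 10%. The mixture adds 0.55²×0.9×0.1×1.25 = 0.0340 to the lucerastat variance. The slopes shrink to −0.495 (arm) and −0.331 (common). Lucerastat variance is 0.0125+0.0340+0.0067 = 0.0532 and placebo variance is 0.0125+0.331²×0.25 ≈ 0.0400. The model SE is 0.0432 and the true SE 0.0412, so coverage is about 96%. The error has changed direction.

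**Simulation of the planned ANCOVA** (log-normal baseline and noise, 2,500 replicates per cell, target the population mean difference; Monte Carlo error about √(0.9×0.1/2500) = 0.6 points):

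| Placebo noise CV | Reverting | Baseline CV 0.3 | 0.5 | 0.8 |
|---|---|---|---|---|
| 10% | 0% | 92.4% | 91.0% | 87.4% |
| 22% | 0% | 87.7% | 87.2% | 85.6% |
| 10% | 10% | 97.4% | 95.7% | 92.8% |
| 22% | 10% | 94.5% | 92.4% | 90.8% |

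A separate run of the second row gave 87.0%, 87.6% and 83.8%. The same ANCOVA with HC3 gave 94.2%, 94.3% and 91.0% there. With 10% of Month 6 values missing and imputed, the planned interval covered 81–87%. Widening placebo noise to 5–30% at 10% reversion gives 89–98%. At 20% reversion and baseline CV 0.5, coverage is 95–97%.

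**Test size.** With no drug effect, two-sided rejection was 4.9% (baseline CV 0.5) and 4.6% (0.8). Rejection was 100% in every −55% scenario.

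**The case against.** The strongest reply is that no decision depends on this interval. The sequence turns on rejecting the null, the test holds its level, and no margin is set on the width of the Gb3 CI. That stands, and it is why the point is minor.

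Second, the inputs transfer imperfectly. The 55% fall comes from Phase 1b at Week 12 on top of ERT, in a programme where only 10 Fabry subjects received lucerastat. This trial is monotherapy to Month 6 under a treatment-policy estimand that expects discontinuation. With the Week 4 figures (−39%, SD 14; Protocol 3.2), coverage is 87–98%. With a lucerastat SD of 20 points and placebo noise of 10%, it is 96–97%. A reader might therefore infer that the reported interval is simply too narrow. The documents do not support that: they report mean percentages without saying that the effect is proportional to baseline, and they omit the quantities that fix the direction of the error.

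Third, SAP 15.3.3 already repeats the analysis on the log ratio, which covers 94.8–95.2% under a proportional effect with equal noise CV. But it is supportive and estimates a ratio, whereas the estimand in SAP 3.4 is a difference in mean change. The CI for that difference stays uncorrected. CR and J2R address missing data only.

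Fourth, the target matters. At placebo noise of 10 points, the planned interval covers the difference at the enrolled subjects' own baselines 96% of the time. At 22 points it still falls to 89–92%. The estimand names the eligible Fabry population, so the population target is the relevant one.

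**Conclusion.** The concern holds conditionally. The model-based 95% CI for the Gb3 mean difference can mis-cover because unequal residual variances and slopes are pooled across 2:1 arms. With a proportional fall of about 55% (SD 10 points) and almost no reversion, coverage is roughly 84–93% over baseline CV 0.3–0.8 and placebo noise CV 10–22%. With 10–20% of lucerastat subjects reverting, it ranges from about 89% to 98%. Baseline CV, placebo noise and reversion are assumptions.

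It would be wrong to infer that the Gb3 test or the fixed sequence is compromised. With no effect, the source of the unequal slopes and scatter examined here is absent, and simulated size is 4.6–4.9%. The weakness is confined to stated precision. Minor severity.

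**What to change.** In SAP 15.3.3, keep the absolute-change endpoint, estimand, model terms and point estimate. Within each imputed dataset, take the standard error of the treatment difference from an HC3-type heteroscedasticity-robust estimator, then combine by Rubin's rules as planned. Simulated coverage is about 93–96% for baseline CV up to 0.7 and about 91% at 0.8. These HC3 figures are for complete data, so a short check through the imputation step is advisable before the code is fixed.

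Do not substitute arm-specific variances plus a treatment-by-baseline term evaluated at the sample mean baseline. That treats the mean baseline as known. At baseline CV 0.5 and placebo noise 10%, its variance is 0.0125/39 + 0.0125/79 = 0.00048. It omits 0.55²×0.25/118 = 0.00064 from sampling the baselines. The SE ratio is √(0.00048/0.00112) = 0.65 and coverage about 80%, against about 91% for the model as written. Across the settings simulated it covered 68–94%, worse than the planned model in most of them.

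The cost is one analysis option. The interval may be up to about 30% wider or about 14% narrower than the model-based one. Because the error can go either way, the robust estimator is useful without knowing the undocumented inputs.
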